10.4 Statistical Analyses

The statistical analysis plan (SAP) will be developed and finalized before database lock and will describe the selection of participants to be included in the analyses and procedures for accounting for missing, unused, and spurious data. Below is a summary of planned statistical analyses of the primary and secondary endpoints.

The SAP will be finalized prior to database lock and it will include a more technical and detailed description of the statistical analyses described in this section. This section is a summary of the planned statistical analyses of the most important endpoints, including primary and secondary endpoints. This section describes all of the planned analyses in this protocol but some of them may not necessarily provide statistically meaningful estimate due to the limited sample size. In such case, the best available summary and/or descriptive statistics will be provided.

A description of the participant population will be included in the clinical study report, including subgroups of age, gender, race, and other study-specific populations and demographic characteristics. A description of participant disposition will also be included in the clinical study report.

10.4.1 General Considerations

The primary and secondary estimands are described in [Table 4-1](#).

10.4.2 Primary Endpoint(s)

The primary efficacy endpoint of RFS is defined as the time from randomization to the date of documented relapse after CR or CRi per central review, or death from any cause, whichever occurs first. Participants who are still alive without documented relapse after CR or CRi, or who were lost to follow-up without documented relapse, will be censored at the date of their last response assessment. Relapse after CR or CRi is defined according the IWG AML response criteria.

The primary efficacy analysis will be conducted for the ITT Population and will compare the RFS distributions between the two treatment groups. A Cox proportional hazards model will be used to estimate the corresponding hazard ratio and 95% CI for CC-486 relative to placebo. The RFS curves will be estimated for the primary efficacy endpoint, time to the date of documented relapse after CR or CRi or death from any cause, whichever occurs first, using Kaplan-Meier (KM) methods. Kaplan-Meier estimates for median RFS as well as the 25th and 75th percentiles and associated two-sided 95% CIs will be summarized for each treatment group. Plots of the KM survival curves will be presented for the two treatment groups.

Additionally, KM methods will be used to estimate the 1-year and 2-year RFS probabilities for time to death from any cause. Estimates of the 1-year (365 days) and 2-year (730 days) survival probabilities and corresponding 95% confidence intervals will be presented by treatment group.

Additional sensitivity analyses, based on the mITT Population and the ITT Population, will be performed using modified RFS definitions. For these analyses of RFS, participants lost to follow-up without documented relapse will be 1) considered as having an event and 2) considered as having an event if they were randomized to the CC-486 treatment group and censored if they were randomized to the placebo treatment group. The event/censoring time will be the date of the last response assessment.

To assess and compare the modified definition of AML relapse being used in this protocol as a criterion for discontinuation from treatment (ie, appearance of > 15% blasts in the bone marrow or peripheral blood) with respect to the IWG definition of relapse after CR or CRi, an exploratory analysis based on the mITT population will be performed for RFS using this modified definition of relapse. For this analysis of RFS, relapse after CR or CRi is defined as the appearance of > 15% blasts in the bone marrow or peripheral blood. Participants who are still alive without documented relapse after CR or CRi or who were lost to follow-up without documented relapse will be censored at the date of their last response assessment.

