10.3 Analysis Sets

For the purposes of analysis, the following populations are defined:

Population	Description
Intent-to-treat (ITT)	All participants who have agreed to participate in the study following completion of the informed consent process and registered into the IRT, regardless of whether they received treatment.
Modified intent-to-treat (mITT)	All participants who have met all inclusion/exclusion criteria and experienced no major protocol deviations during the study, and received a minimum of 1 cycle of treatment. Participants who are registered without confirmed CR/CRI per central review will be excluded from the mITT population.
Safety	All participants who received at least 1 dose of study intervention.
Pharmacokinetic (PK)	All participants who received at least 1 dose of study intervention and have measurable plasma concentration data. All analysis of PK data will be based on the PK population.
Health-related Quality of Life	All participants in the ITT Population with a valid health-related quality of life assessment at baseline and at least 1 valid post-baseline assessment.

Abbreviations: CR, complete remission, CRI, complete remission with incomplete blood count recovery; IRT, Interactive Response Technology; ITT, intent-to-treat; mITT, modified intent-to-treat; PK, pharmacokinetic.

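### The >15% blast RFS is planned only in mITT and IWG RFS under the same censoring rule only in ITT, so relapse definition and population change together

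*Combined protocol and SAP*

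**What the plan says.** The relevant text is in protocol sections 10.4.2 and 10.3.

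- **Primary RFS.** "The primary efficacy analysis will be conducted for the ITT Population". On the criterion: "Relapse after CR or CRi is defined according the IWG AML response criteria". Participants alive without relapse, or lost to follow-up without relapse, are censored at their last response assessment.
- **Sensitivity analyses.** "Additional sensitivity analyses, based on the mITT Population and the ITT Population, will be performed using modified RFS definitions". The text describes a change only in how loss to follow-up is handled. Such participants count as events in both arms (analysis 1), or as events in the CC-486 arm and censored in the placebo arm (analysis 2). No change to the relapse criterion is described.
- **Exploratory analysis.** Its aim is "To assess and compare the modified definition of AML relapse being used in this protocol as a criterion for discontinuation from treatment" against the IWG definition. To that end, "an exploratory analysis based on the mITT population will be performed for RFS using this modified definition of relapse". For it, "relapse after CR or CRi is defined as the appearance of > 15% blasts in the bone marrow or peripheral blood", and participants "who were lost to follow-up without documented relapse will be censored at the date of their last response assessment".
- **Populations (10.3).** ITT is everyone who consented and was registered in the IRT, treated or not. mITT requires that all eligibility criteria were met, that no major deviation occurred during the study, and that the participant "received a minimum of 1 cycle of treatment". It also drops participants whose CR/CRi was not confirmed by central review.

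**The concern.** A comparison of two relapse definitions should apply both to the same people under the same censoring rule, so that only the definition differs. As written, the >15% result comes from mITT, and the IWG result with matching censoring comes from ITT. Part of any gap between the two hazard ratios or Kaplan-Meier curves may then come from who was left out.

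Two of the mITT conditions, absence of major deviations and at least one cycle received, are settled after randomization and need not act equally in the two arms. With about 10 and 5 participants, one or two exclusions are a visible share of the data. What is at stake is how clearly the plan's own question about the >15% threshold is answered. No efficacy claim rests on it.

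**Working it through.** **Step 1. The analyses side by side (section 10.4.2).**

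| Analysis | Relapse criterion | Population | Lost to follow-up |
|---|---|---|---|
| Primary | IWG | ITT | Censored, both arms |
| Sensitivity 1 | IWG | mITT and ITT | Event, both arms |
| Sensitivity 2 | IWG | mITT and ITT | Event in CC-486, censored in placebo |
| Exploratory | >15% blasts | mITT | Censored, both arms |

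The exploratory row needs a partner with IWG relapse, mITT, and censoring in both arms. None is listed. The primary analysis differs from it in population as well as criterion. Sensitivity 1 matches in population but differs in loss-to-follow-up handling in both arms. Sensitivity 2 matches in the placebo arm and differs in the CC-486 arm. Sensitivity 1 becomes a full partner if nobody in mITT is lost to follow-up, and sensitivity 2 if no CC-486 participant in mITT is.

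**Step 2. What a same-set comparison would isolate.** Appendix 6 defines relapse as leukemic blasts reappearing in blood, or at least 5% blasts in marrow, not due to another cause. Relapse above 15% in blood or marrow meets that definition too, so a participant's >15% relapse should not precede the IWG relapse. In one population, the two results differ only through participants who relapse by IWG criteria while still at or below 15%. Sections 5.1 and 7.4.2 allow participants with 5% to 15% blasts to stay on treatment, so this group may exist. Among 15 people it will be small, and a change of population can easily mask it.

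**Step 3. The plan's own figure, to check the model used in step 4.** Section 10.2 gives 87% as the probability that the estimated hazard ratio is below 1. Inputs: medians of 4.8 and 9.5 months (10.1) and 2:1 allocation (10.2). The number of events d is not stated.

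- HR = 4.8/9.5 = 0.505, so |ln HR| = 0.683
- P(estimate < 1) = Φ(|ln HR| × √(d × 2/3 × 1/3))
- d = 12: Φ(0.683 × √2.667) = Φ(1.115) = 86.8%
- d = 11 gives 85.7%; d = 13 gives 87.7%

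With exponential RFS, 12 months of follow-up after the last participant (10.1) and an assumed 18 months of uniform accrual, 12.4 events are expected and the formula gives 87.1%. The plan's figure is reproduced, and this point does not affect it.

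**Step 4. How far can a population change alone move the estimate?** This is an illustration under assumptions: the step 3 model, 10 and 5 participants, 18 months of accrual, the same relapse definition in both sets, and k participants removed at random. There were 5,000 simulated trials; non-finite Cox estimates were set aside. The documents give no value for k.

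| k removed of 15 | Share | Median factor of change in HR | 90th percentile | Estimate crosses HR = 1 |
|---|---|---|---|---|
| 1 | 6.7% | 1.15 | 1.32 | 4% |
| 2 | 13.3% | 1.20 | 1.56 | 7% |
| 3 | 20.0% | 1.28 | 1.85 | 10% |

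The factors measure movement in either direction. They are not a predicted bias.

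**The case against.** The best case for the plan has four parts.

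- **IWG relapse is already analysed in mITT.** This is correct. A reader might infer that mITT has no IWG-based RFS at all, and the documents do not support that. Sensitivity 2 matches the exploratory analysis in the placebo arm and would match fully if no CC-486 participant in mITT were lost to follow-up. What stands is that the match depends on how follow-up turns out.
- **The comparator is not named.** Section 10.4.2 does not say that the >15% result will be set against the ITT result, and section 10.4 leaves the selection of participants to the SAP. That is fair. However, section 10.4 also says it describes all planned analyses. The mITT restriction is explicit, and no IWG analysis in mITT under the same rule is listed.
- **The definitions can be compared person by person.** Both apply to the same blast data in about 15 people, and Table 3.3.1-1 commits to looking at efficacy in individual subjects. So a reader who concludes that the plan's question cannot be answered goes too far.
- **mITT is a defensible set for this purpose.** Relapse after CR/CRi is hard to interpret when remission was never confirmed centrally. This is a reason to keep mITT as an additional set. It is no reason to compare across two sets.

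It is also tempting to size the effect by assuming that every RFS event in the first 28 days removes a participant from mITT. The documents do not support this. An IWG relapse does not by itself end treatment, because mandatory discontinuation for relapse applies above 15% blasts (8.1). The first scheduled on-treatment marrow is at Cycle 3 (9.1.1). Under an exponential model, conditioning both arms on the same early event-free period would also leave the hazard ratio unchanged.

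**Conclusion.** The point holds as a mismatch between the stated aim and the planned pair of analyses. Apart from the partial and conditional matches in the sensitivity analyses, definition and population change together, and a difference between the two RFS results cannot be attributed cleanly to the blast threshold.

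The size cannot be fixed from the documents, because the number leaving mITT is not given. The factors of 1.15 to 1.28 rest on an assumed 1 to 3 random exclusions, exponential RFS and 18 months of accrual. Real exclusions would not be random. The figures show only that a sample this small is sensitive to the choice of population.

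The importance is low: the analysis is exploratory, section 10.1 plans no hypothesis test, and the primary result does not change.

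**What to change.** State in the SAP, before database lock:

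1. The >15% blast RFS is run in ITT with the censoring rule of the primary analysis and shown beside the primary IWG result.
2. If mITT is kept for the >15% analysis, IWG RFS is also run in mITT under that same rule, so that the two definitions are always compared in the same participants.
3. Whether >15% relapse is judged by central review, as primary relapse is. The exploratory text does not say.
4. One censoring rule by name. Section 10.4.2 uses the last response assessment, while section 10.1 uses the last contact date or last known RFS date. The pairing works only if both analyses follow the same one.

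A short listing of participants whose event date or status differs between the two definitions would be a useful addition.

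The cost is a few sentences and one or two further runs of an existing program. No new data are needed, and trial conduct does not change.

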10.4.3 Secondary Endpoint(s)

Overall Survival

The secondary efficacy endpoint of OS is defined as the time from randomization to death from any cause and will be calculated using the randomization date and date of death, or date of last follow-up for censored participants. All participants will be followed until dropout, death, or study termination. Participants who dropout or are alive at study termination will have their OS times censored at the time of last contact, as appropriate. OS analysis will be conducted for the ITT population.

Safety

All safety analyses will be performed on the Safety Population. Adverse events will be coded using the Medical Dictionary for Regulatory Activities (MedDRA). Adverse event listings will include the verbatim term and the MedDRA preferred term. Treatment-emergent adverse events (TEAEs) will be summarized by worst severity grade, system organ class, and preferred term. Treatment-emergent AEs leading to death or to discontinuation from treatment, AEs classified as NCI-CTCAE (Version 5.0) Grade 3 or Grade 4, AEs related to IP, and SAEs will be summarized separately. Time to discontinuation from the study due to AE will be summarized using KM methods. Listings of all deaths and all SAEs, regardless of when they occurred, will also be generated.

Pharmacokinetics

The sparse concentration-time data collected in this study may be combined with a larger dataset to help further develop and validate the population pharmacokinetic model for azacitidine and to aid in the identification of covariates that influence azacitidine pharmacokinetic and/or pharmacodynamic measures and efficacy and safety endpoints. PK population will be used for PK analysis. Noncompartmental analysis will be performed using intensive sampling data.

Health-related Quality of Life

PRO endpoints include FACIT-Fatigue and the EQ-5D-5L, and analyses will include the Health-related Quality of Life population. Summary statistics (N, mean with SD and 95% CI, median, first and third quartiles, minimum, maximum) for PRO measures at each assessment point will be provided for each treatment arm. The mean change from baseline will also be reported at each post-baseline assessment point. Additionally, for the EQ-5D-5L, the proportion of participants endorsing each response option will be calculated at each time point.

Health utility scores as assessed by the EQ-5D-5L will be derived for each subject using country-specific weights (primary analysis will be done using UK weights). Using EQ-5D-5L scoring instructions, utility and VAS scores will be analyzed using the change from baseline assessment at each post-screening time point.

Additional details will be provided in the SAP.

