A separate central review of all bone marrow aspirates, bone marrow biopsies, and peripheral blood smears will be conducted by a pathologist blinded to participant treatment. The central reviewer's assessments will be used to confirm the CR/CRI status at screening and during treatment for maintenance assessment. If the central reviewer and local pathologist disagree on the CR/CRI status of a participant, a third-party reviewer will adjudicate and make the final assessment.

The central cytogenetic review will provide standardized analysis and reporting for all participants, regardless of the laboratory performing the initial analysis (local or central).

[figure not shown]
In participants on study who have subsequent evidence of AML relapse with blasts \geq 5%, either in the peripheral blood or bone marrow, and provided the blasts are no greater than 15% in the blood or bone marrow, escalation of the dosing regimen (dose and/or schedule) can be implemented ([Section 7.4.2](#)).

Participants will be discontinued from treatment when they meet the following criteria:

- Appearance of > 15% blasts in the bone marrow or peripheral blood.
- The above occurrence should be attributed to relapse following CR/CRI and not attributable to any other cause (eg, bone marrow regeneration after consolidation therapy).

All discontinued participants, regardless of reason for discontinuation, should undergo Treatment Discontinuation Visit procedures at the time of study discontinuation. Participants will have a follow-up visit for the collection of AEs up to 28 days after last dose of IP or up to the Treatment Discontinuation Visit, whichever is longer. After this follow-up visit, participants will be followed for survival every month for the first year and then every 3 months until death, withdrawal of consent for further follow-up, until a participant is lost to follow-up or study end, or when the commercial product of CC-486 becomes available at the site, whichever comes first.

Figure 5.1-1: Study Design Schema

^aIWG 2003; assessment for CR/CRI or relapse at the Cycle 3; if CC-486 treatment continues, response assessed every 3rd cycle (ie, Cycles 6, 9, 12, etc).
^bFor participants receiving the initially assigned dose level and schedule.

alloSCT, allogeneic stem cell transplantation; AML, acute myeloid leukemia; APL, acute promyelocytic leukemia; BM, bone marrow; BSC, best supportive care;

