The starting dose for participants is 200 mg CC-486 or placebo QD for the first 14 days of each 28-day treatment cycle. This CC-486 dose and schedule have demonstrated tolerability and shown signs of clinical activity in a prior study the ORACLE study. Participants should continue to receive CC-486 for at least 2 cycles of treatment before being assessed for discontinuation from the study due to disease relapse at the early timing of efficacy evaluation.

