8 DISCONTINUATION CRITERIA

8.1 Discontinuation From Study Intervention

Participants MUST discontinue IP (and Non-IP/AxMP at the discretion of the investigator) for any of the following reasons:

- Disease relapse

Participants will be discontinued from treatment when they meet the following criteria:

- Appearance of > 15% blasts in the bone marrow or peripheral blood
- The above occurrence should be attributed to relapse following CR/CRi, and not attributable to any other cause (eg, bone marrow regeneration after consolidation therapy or myeloid growth factor administration).

- Participant's request to stop study intervention. Participants who request to discontinue study intervention will remain in the study and must continue to be followed for protocol-specified follow-up procedures. The only exception to this is when a participant specifically withdraws consent for any further contact with him/her or persons previously authorized by the participant to provide this information
- Any clinical AE, laboratory abnormality, or intercurrent illness which, in the opinion of the investigator, indicates that continued participation in the study is not in the best interest of the participant
- Participant withdraws from active treatment but continues follow-up
- Participant becomes eligible (per Investigator) for allogeneic bone marrow or stem cell transplantation during the treatment period
- Death
- Loss to follow up
- Protocol violation
- Termination of the study by BMS
- Loss of ability to freely provide consent through imprisonment or involuntarily incarceration for treatment of either a psychiatric or physical (eg, infectious disease) illness. (Note: Under specific circumstances and only in countries where local regulations permit, a participant who has been imprisoned may be permitted to continue as a participant. Strict conditions apply, and BMS approval is required.)

Refer to the [Schedule of Activities](#) for data to be collected at the time of treatment discontinuation and follow-up and for any further evaluations that can be completed.

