All participants who discontinue study intervention should comply with protocol-specified follow-up procedures as outlined in [Section 2](#). The only exception to this requirement is when a participant withdraws consent for all study procedures, including post-treatment study follow-up, or loses the ability to consent freely (eg, is imprisoned or involuntarily incarcerated for the treatment of either a psychiatric or physical illness). Additionally, all participants who are discontinued from protocol-prescribed treatment will be followed for a period of 28 days following

the last dose of IP or until the date of the last study visit, whichever is later, for the collection of AEs. Discontinued participants will not be replaced.

If study intervention is discontinued prior to the participant's completion of the study, the reason for the discontinuation must be documented in the participant's medical records per local regulatory requirements in each region/country and entered on the appropriate CRF page.

8.1.1 *Post-study Intervention Study Follow-up*

In this study, RFS is the primary endpoint of the study. Post-study follow-up is of critical importance and is essential to preserving participant safety and the integrity of the study. Participants who discontinue study intervention must continue to be followed (in this study or a rollover study) for collection of outcome and/or survival follow-up data as required and in line with [Section 5](#) until death or the conclusion of the study.

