8.2 Discontinuation From the Study

Participants who request to discontinue study intervention will remain in the study and must continue to be followed for protocol-specified follow-up procedures. The only exception to this is when a participant specifically withdraws consent for any further contact with him/her or persons previously authorized by participant to provide this information.

- Participants should notify the investigator of the decision to withdraw consent from future follow-up.
- The withdrawal of consent should be explained in detail in the medical records by the investigator, as to whether the withdrawal is from further treatment with study intervention only or also from study procedures and/or post-treatment study follow-up, and entered on the appropriate CRF page.
- In the event that vital status (whether the participant is alive or dead) is being measured, publicly available information should be used to determine vital status only as appropriately directed in accordance with local law.
- If the participant withdraws consent for disclosure of future information, the Sponsor may retain and continue to use any data collected before such a withdrawal of consent.

8.2.1 *Individual Discontinuation Criteria*

- A participant may withdraw completely from the study at any time at his/her own request, or may be withdrawn at any time at the discretion of the investigator for safety, behavioral, compliance, or administrative reasons. This is expected to be uncommon. Stopping study intervention is not considered withdrawal from the study.
- At the time of discontinuing from the study, if possible, an early termination visit should be conducted, as shown in the Schedule of Activities. See the Schedule of Activities for data to be collected at the time of study discontinuation and follow-up and for any further evaluations that need to be completed.

- The participant will be permanently discontinued both from the study intervention and from the study at that time.
- If the participant withdraws consent for disclosure of future information, the Sponsor may retain and continue to use any data collected before such a withdrawal of consent.

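### Minor: the planned Kaplan-Meier summary of discontinuation due to AE names the study where treatment is meant, and gives no rule for relapse and death, which also end treatment

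*Combined protocol and SAP*

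**What the plan says.** The analysis is one sentence in the Safety part of Section 10.4.3: "Time to discontinuation from the study due to AE will be summarized using KM methods". The paragraph sets the Safety Population. It gives no event definition, time origin or censoring rule for this display. The sentence before it plans a separate summary of treatment-emergent AEs that lead to death or to stopping treatment.

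Section 8 separates stopping IP from leaving the study:

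- Section 8.1 lists, among the reasons for stopping IP, "Any clinical AE, laboratory abnormality, or intercurrent illness which, in the opinion of the investigator" makes continuing not in the participant's best interest.
- The same list contains relapse, defined as "Appearance of > 15% blasts in the bone marrow or peripheral blood", together with death, loss to follow-up, transplant eligibility and "Termination of the study by BMS".
- After a stop, "All participants who discontinue study intervention should comply with protocol-specified follow-up procedures".
- Section 8.2.1 allows an investigator to withdraw a participant from the study for safety, among other reasons, but adds: "This is expected to be uncommon. Stopping study intervention is not considered withdrawal from the study".

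Table 4-1 gives the proportion of patients with an event as the safety summary statistic. Section 10.4 leaves technical detail to a later SAP and allows simpler summaries where the sample is too small for a meaningful estimate.

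**The concern.** There are two linked problems.

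**The event.** Taken word for word, the sentence counts people who leave the study because of an AE. Section 8 keeps people who stop IP for an AE in follow-up and expects withdrawal from the study to be uncommon. A programmer who follows the wording would produce an almost empty display that does not match the summary of AEs ending treatment beside it.

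**The method, once treatment stop is understood.** A participant taken off treatment for relapse, or who has died, can no longer stop treatment for an AE. Censoring such exits in a KM estimate answers a different question from what share of the arm stopped for an AE. Because relapse is planned to be faster on placebo, the gap would differ by arm, in a study that relies on descriptive safety data from about 10 and 5 participants.

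**Working it through.** **Step 1: which event is meant.** Other sections use the word study for events that are treatment stops:

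- Section 5.1: discontinued participants "should undergo Treatment Discontinuation Visit procedures at the time of study discontinuation".
- Section 5.4: participants receive at least 2 cycles "before being assessed for discontinuation from the study due to disease relapse".
- Section 8.1: the AE bullet in the list of reasons for stopping IP itself speaks of continued participation in the study.

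All three fit treatment stop. So does the neighbouring sentence in Section 10.4.3.

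**Step 2: whether another passage supplies the rule.** It does not. Table 4-1 lists relapse, death and subsequent therapy as intercurrent events for a different endpoint, all-cause time to treatment discontinuation, and gives no strategy for them. For safety, Table 4-1 uses treatment policy, that is, data after the intercurrent event are kept. That cannot be applied here, because no AE stop can follow once treatment has ended.

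**Step 3: arithmetic at trial scale, with no assumed rate.** With n participants and one AE stop after k censored exits, 1-KM = 1/(n-k), while the observed proportion is 1/n.

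| Arm | k | 1-KM | Observed |
|---|---|---|---|
| Placebo, n=5 | 0 | 20% | 20% |
| Placebo, n=5 | 2 | 33% | 20% |
| Placebo, n=5 | 3 | 50% | 20% |
| CC-486, n=10 | 0 | 10% | 10% |
| CC-486, n=10 | 2 | 12.5% | 10% |
| CC-486, n=10 | 5 | 20% | 10% |

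With no AE stop, both are 0.

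**Step 4: constant hazards to 12 months.** Inputs:

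- Planned median RFS of 9.5 months (CC-486) and 4.8 months (placebo), from Section 10.1.
- AE-stop hazard a of 0.005 to 0.04 per month. This is an assumption; the documents give no rate.
- Other exits at hazard r = f × ln 2 / median, with f = 1 or 0.5. The lower value is also an assumption. It allows for treatment ending only above 15% blasts (Section 8.1), whereas RFS uses the International Working Group relapse definition, which includes marrow blasts of 5% or more (Section 10.4.2, Appendix 6).

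Formulas: 1-KM = 1 - exp(-12a). Cumulative incidence = a/(a+r) × [1 - exp(-12(a+r))].

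Worked case, f = 1:

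- CC-486, a = 0.02, r = 0.0730: 1-KM = 21.3%, cumulative incidence = 14.5%, ratio 1.48.
- Placebo, a = 0.01, r = 0.1444: 1-KM = 11.3%, cumulative incidence = 5.5%, ratio 2.07.

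Ratios over the whole range of a:

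| | f = 1 | f = 0.5 |
|---|---|---|
| CC-486 | 1.45 to 1.49 | 1.21 to 1.23 |
| Placebo | 1.97 to 2.09 | 1.45 to 1.49 |

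**Step 5: early AE stops.** Now let the AE-stop hazard be 0.02 per month for 3 months and zero afterwards (assumption). Then 1-KM = 1 - exp(-0.06) = 5.8%. Cumulative incidence on CC-486 is 5.2% (f = 1) or 5.5% (f = 0.5), ratios 1.11 and 1.06. On placebo it is 4.7% or 5.2%, ratios 1.23 and 1.11.

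**Step 6: how many AE stops to expect.** In the worked case of Step 4, the expected number is 10 × 0.1446 + 5 × 0.0546 = 1.7. The chance of no AE stop by 12 months is (1 - 0.1446)^10 = 21% on CC-486 and (1 - 0.0546)^5 = 76% on placebo.

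**The case against.** The strongest case against is that this is a one-word clarification. The intended event can be recovered from the protocol's own usage. Time origin and censoring are left to an SAP not yet written, and Section 10.4 already provides a descriptive fallback. A KM that censors other exits is a valid cause-specific summary and need not equal a crude proportion. AE stops may also come early: the first scheduled response assessment is at Cycle 3 (Section 9.1.1), and Section 5.4 asks for at least 2 cycles before discontinuation for relapse is considered.

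Much of this stands. A reader might infer that the planned display will be near-empty. The documents do not support that, because Sections 5.1, 5.4 and 8.1 show that treatment stop is meant. A reader might also infer that KM is wrong here, or that a twofold distortion on placebo is to be expected. Neither follows: the larger ratios need constant AE-stop hazards and an RFS-based exit rate, and in the worked example the placebo arm has no AE stop three times in four.

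What does not stand is that deferral settles the matter. By Section 10.4 the SAP will detail the analyses described in that section, so an event named wrongly there would be carried forward. The safety statistic the plan itself names is a proportion, and cumulative incidence is the time-to-event form that agrees with it.

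**Conclusion.** The point holds and is minor. The sentence in Section 10.4.3 should refer to discontinuation from treatment, and it needs a time origin and a rule for other exits. If relapse and death are censored, 1-KM overstates the share who stop treatment for an AE:

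- by nothing, if AE stops precede every other exit;
- by about 1.06 to 1.23-fold, if they fall in the first 3 months at an assumed 0.02 per month;
- by up to about 1.5-fold on CC-486 and 2.1-fold on placebo at 12 months, under constant hazards with exits at the full planned RFS rate.

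All rates of AE stopping are assumptions. The effect is confined to one descriptive display in about 15 participants. AEs leading to treatment discontinuation are already summarised, and all-cause time to treatment discontinuation is already a secondary endpoint, so this display adds only the timing of AE stops. A reader might infer that the efficacy results are touched. They are not: RFS and the 87% probability in Section 10.2 do not use this quantity.

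**What to change.** Replace the sentence, in Section 10.4.3 or in the SAP, with:

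> In the Safety Population, time from first dose to discontinuation from treatment with AE (including fatal AE) as the recorded primary reason will be summarised by treatment group with the cumulative incidence function (Aalen-Johansen). Permanent treatment discontinuation for any other recorded reason, including relapse and death not due to an AE, will be a competing event. Participants still on treatment at data cut-off, lost to follow-up, or stopped by study termination will be censored. Counts and a listing by reason will accompany it.

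Using the recorded primary reason matters. An AE stop under Section 8.1 is itself an investigator's judgement, so a competing category for investigator decision would overlap with the event. It also places stops that follow a long cycle delay (Section 7.4.3) according to the reason entered.

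If AE stops are too few for a useful curve, the counts and listing are enough, as Section 10.4 allows.

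The cost is one sentence and a little programming. Stop dates (Section 7.6) and the reason for discontinuation (Section 8.1) are already collected on the CRF, and no clinical rule changes.
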